**10.3.3 Pharmacokinetic Analysis for BMS-986288**

See Table 10.3.3-1 for PK statistical analyses.

**Table 10.3.3-1: Pharmacokinetic - Statistical Analyses**

Endpoint	Statistical Analysis Methods
Cmax, AUC(0-T), AUC(TAU), Ctau, CLT, Css-avg, AI_Cmax, AI_AUC, and T-HALF	Summary statistics: geometric means and coefficients of variation
Cmax, AUC(0-T), AUC(TAU)	Scatter plots vs dose for each cycle measured; dose proportionality based on a power model and a CI around the power coefficient
Tmax	Summary statistics: medians and ranges
Ctrough	Summary statistics to assess attainment of steady state: geometric means and coefficients of variation, by treatment and by day; plots vs time by dose

Abbreviations: AI\_AUC = ratio of an exposure measure at steady state to that after the first dose (exposure measure includes AUC[TAU]); AI\_Cmax = ratio of an exposure measure at steady state to that after the first dose (exposure measure includes Cmax); AUC(0-T) = area under the plasma serum concentration-time curve from time zero to time of last quantifiable concentration (may be calculated if concentrations are not quantifiable up to TAU across a treatment group); AUC(TAU) = area under the serum concentration-time curve in 1 dosing interval; CLT = total body clearance; Cmax = maximum observed concentration; Css-avg = average serum concentration over a dosing interval (AUC[TAU]/tau) at steady state; Ctau = observed serum concentration at the end of a dosing interval; Ctrough = trough observed serum concentrations (this includes predose concentrations [C0] and Ctau); T-HALF = terminal serum half-life; Tmax = time of maximum observed plasma serum concentration.

A non-compartmental or PPK approach will be used to assess the PK data and parameters such as Cmax, AUC(0-T), and bioavailability (F) will be assessed as feasible and applicable. PK concentration-time data for BMS-986288, and sparse plasma concentration-time for nivolumab

may be pooled with data from other studies for integrated PPK and ER analyses, which will be presented in a separate report.

#### **10.3.4 Immunogenicity**

Endpoint	Statistical Analysis Methods
Incidence of anti-drug antibodies (ADAs) Baseline ADA-positive participant is defined as a participant who has an ADA-detected sample at baseline a,b ADA positive-participant is a participant with at least 1 ADA-positive sample relative to baseline after initiation of the treatment	Frequency distribution of baseline ADA-positive participants and ADA-positive participants after initiation of the treatment

a Baseline sample is the last sample before initiation of the treatment.

b Details of the immunogenicity data analysis, including ADA titers, will be provided in the Statistical Analysis Plan.

#### **10.3.5 Biomarker Analyses**

Endpoint	Statistical Analysis Methods
Summary measures of change (or % change) from baseline in various biomarkers in the [REDACTED]	Summary statistics/plots by planned study day and dose in each arm Plots of the time course of biomarkers

#### **10.3.6 ECG Analyses**

All ECG data analyses including summaries of each ECG parameter, frequency distribution of participants' maximum values/changes, and scatter plots will be performed following the current practice of ECG data analysis. Concentration-response analysis may be performed using mixed effect model, if appropriate. The details of ECG data analysis will be provided in the Statistical Analysis Plan.

#### **10.3.7 Other Analyses**

Pharmacodynamic biomarker exploratory analyses and exploratory analyses of clinical outcomes assessments will be described in detail in the Statistical Analysis Plan finalized before database lock. OSR at 1 year and 2 years will be analyzed similarly to PFS. The population PK/ER and pharmacodynamic analyses may be presented separately from the main Clinical Study Report.

#### **10.3.8 Interim Analyses**

Interim analyses will be performed for administrative purposes or publication. No formal inferences requiring any adjustment to statistical significance level will be performed.

Preliminary efficacy may be assessed for Part 2 to determine an initial signal, and enrollment may be paused, prior to enrolling additional participants. If an inadequate signal is detected from a preliminary analysis, then enrollment may be closed for that cohort.

### **10.3.8.1 Bayesian Continuous Monitoring for Treatment-related Toxicities Meeting DLT Criteria in Part 2**

A Bayesian continuous monitoring framework will be used to ascertain safety signals that occur during Part 2 that may lead to suspension or evaluation of toxicity by the Sponsor/Medical Monitor in BMS-986288 as a monotherapy and/or in combination with nivolumab participants. Incidence rates of treatment-related toxicities meeting DLT criteria (defined in [Section 7.4.1](#)) are compared to 33%.

The Bayesian safety monitoring boundaries are established using a noninformative prior, Beta (0.5, 0.5). The posterior distribution is Beta ( $0.5+n$ ,  $0.5+[m-n]$ ), where  $m$  is number of treated Part 2 participants per dose level and  $n$  is the subset of these  $m$  participants who experience treatment-related toxicities meeting DLT criteria. All treated Part 2 participants are considered evaluable. The criterion for not continuing for future participants is based on the posterior probability of (treated Part 2 participants who experience treatment-related toxicities meeting DLT criteria  $> 33\% \mid$  cumulative data)  $> 0.80$ . This criterion implies that continuation of BMS-986288 as a monotherapy and/or in combination with nivolumab at that dose level in Part 2 will be re-evaluated if there is greater than 80% probability that the number of participants with treatment-related toxicities meeting DLT criteria is larger than 33%, corresponding to a final boundary of 16 out of 40 total participants. When the stopping boundaries shown in Table 10.3.8.1-1 are met, further enrollment at that expansion dose level will be temporarily halted. Recommendations from interim calculations, and the totality of the data will be reviewed by the independent SMT. Based on the SMT's review, the current dose level may be permanently discontinued, and a lower dose level will be evaluated in the remaining study part. Similar continuous safety monitoring will be applied to the new dose level being evaluated.

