#### **7.4.1 Dose-limiting Toxicities**

For the purpose of guiding dose escalation, all AEs will be assessed and DLTs will be defined based on the incidence, intensity, and duration of the AEs for which no clear alternative cause is identified. The DLT period will be 5 weeks (35 days) in both BMS-986288 monotherapy and combination dose escalation (Part 1A and Part 1B). Any toxicities that occur beyond the DLT period will be accounted for in making final dose level decisions. Participants who have discontinued due to a DLT or who have received 2 doses of BMS-986288 monotherapy or in combination with nivolumab and have completed the 5-week DLT period will be considered as DLT-evaluable participants. Participants who withdraw from the study during the DLT evaluation period or have received less than 2 doses for reasons other than a DLT in both monotherapy and combination therapy will not be considered as DLT-evaluable participants and may be replaced with a new participant at the same dose level. Participants who are dose delayed during the DLT evaluation period for reasons other than a DLT in both monotherapy and combination therapy will be considered as DLT-evaluable participants if they received at least 2 doses of therapy within 8 weeks.

For the purpose of participant management, any drug related AE that meets DLT criteria, regardless of the cycle or cohort in which it occurs, will lead to discontinuation of study treatment.

AEs will be graded according to the NCI CTCAE v5.0.

Continuous evaluation of toxicity events in the [REDACTED] Evaluation of BMS-986288 [REDACTED] and BMS-986288 Cohort Expansion Combination Therapy (Part 2) will be performed. If at any time, the aggregate rate of treatment-related toxicities meeting DLT criteria in a BMS-986288 containing cohort exceeds 33% across patients treated in a cohort, the findings will be discussed with the Investigators and further enrollment may be interrupted. If a cohort is discontinued due to toxicity, a new cohort at a previously tested alternative dose level which was found to be safe in Part 1A or Part 1B may be considered based on the aggregate safety experience and in consultation and agreement between Investigators and Sponsor. An alternative dose or administration schedule may also be initiated in a specific [REDACTED] or Part 2 cohort upon

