**Table 10.3.8.1-1: Monitoring Boundaries for Treatment-related Toxicities Meeting DLT Criteria in Part 2**

Number of Evaluable Participants: Treated Part 2 Participants (Cumulative)	Critical Region: At or Above Number of Part 2 Participants Who Experience Treatment-related Toxicities Meeting the DLT Criteria (Defined in Section 7.4.1)
1	
2	
3	
4	
5	
6	
7	
8	
9	
10	
11	
12	
13	
14	
15	
16	
17	
18	
19	
20	
21	
22	
23	
24	
25	
26	
27	
28	
29	
30	
31	
32	
33	
34	
35	
36	
37	
38	
39	
40	

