**Table 10.3.8.1-1: Monitoring Boundaries for Treatment-related Toxicities Meeting DLT Criteria in Part 2**

Number of Evaluable Participants: Treated Part 2 Participants (Cumulative)	Critical Region: At or Above Number of Part 2 Participants Who Experience Treatment-related Toxicities Meeting the DLT Criteria (Defined in Section 7.4.1)

Abbreviation: DLT = dose-limiting toxicity.

These boundaries can be applied on a continuous basis and are intended to assist the clinical interpretation. Other parameters may be considered and other posterior probabilities and boundaries may be calculated. Recommendations from interim monitoring calculations are not binding, and the totality of the data will be considered for decisions by SMT.

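### The Part 2 toxicity boundary counts just-dosed participants as completed non-events, so it is crossed late while follow-up is pending: slightly late at slow accrual, much later at fast accrual

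*Combined protocol and SAP*

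**What the plan says.** Section 10.3.8.1 uses a Beta(0.5, 0.5) prior and the posterior Beta(0.5+n, 0.5+[m-n]). Here m is the number of Part 2 participants treated at the dose level and n is the number of those with a treatment-related toxicity meeting DLT criteria. On who counts in m, it says "All treated Part 2 participants are considered evaluable". Table 10.3.8.1-1 is indexed by the same cumulative treated count, and the text below it allows continuous application.

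The criterion is a posterior probability above 0.80 that the rate exceeds 33%, "corresponding to a final boundary of 16 out of 40 total participants". When the boundary is met, "further enrollment at that expansion dose level will be temporarily halted" and the SMT reviews the data. The closing text adds that "Recommendations from interim monitoring calculations are not binding" and that "Other parameters may be considered and other posterior probabilities and boundaries may be calculated".

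Section 7.4.1 sets a 5-week DLT period and a definition of DLT-evaluable participants, but for the Part 1A and 1B escalation. A few entries in Table 7.4.3.1-1 carry their own timing, such as Cycle 1 for anemia and neutropenia. Neither section gives a general Part 2 observation window, a minimum follow-up or a weight for incomplete follow-up. Section 7.4.1 also has a separate trigger for when the aggregate rate "exceeds 33% across patients treated in a cohort, the findings will be discussed with the Investigators and further enrollment may be interrupted".

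**The concern.** A toxicity can be counted only after it has occurred, but the participant enters the denominator at first dose. Everyone still at risk of a first event is credited as if observation were over. This lowers the posterior and can never raise it. The size of the error follows the share of m that is still pending, so it grows with accrual speed and with later onset.

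Crossing this boundary is the stated trigger for pausing enrolment at an expansion dose. If it is crossed late, more participants start a dose whose toxicity rate is already above the level the rule was built to detect. The SMT also sees a reassuring figure at the time when enrolment is fastest.

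**Working it through.** **Reproducing the plan's figure.** With P(rate > 0.33) taken from Beta(0.5+n, 0.5+m-n):
- 15/40: Beta(15.5, 25.5) gives 0.731, not crossed.
- 16/40: Beta(16.5, 24.5) gives 0.827, crossed.

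The stated 16/40 is confirmed. The table's other entries are blank in the public text and were rebuilt from this formula.

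**One static example.**
- 5 toxicities in 10 fully followed: Beta(5.5, 5.5) gives 0.872, crossed.
- Add 10 dosed one week ago, as written: m = 20, Beta(5.5, 15.5) gives 0.227, not crossed.
- Same data, each new participant counted as 1/12 of a 12-week window: the non-event total is 5 + 10/12 = 5.83, and Beta(5.5, 6.33) gives 0.823, crossed.

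Put another way, with 20 treated the rule needs 9 toxicities. The 10 with complete follow-up would need 5 on their own.

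**Simulation.** Inputs from the plan: prior, 33%, 0.80, cap of 40. Assumed inputs:
- Poisson accrual per dose level, because the documents give no rate.
- Truncated-exponential onset with median 4.6 and maximum 12 weeks. Section 5.5.1 gives a median of 4.6 weeks for Grade 2-4 events, and most immune-related events within 12 weeks, for ipilimumab in melanoma. These are not DLT-criteria events with BMS-986288.

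The weighted version keeps the table from participant 1. From participant 10 it adds the posterior Beta(0.5+n, 0.5+sum of weights), where each event-free participant's weight is the fraction of 12 weeks completed. A trial that does not cross during enrolment counts as 40 treated.

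True rate 45%:

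| Accrual per week | Mean treated, as written | Mean treated, weighted | Crossed only after all 40 treated, as written | Same, weighted |
|---|---|---|---|---|
| 0.25 | about 13 | about 12 | – | – |
| 0.5 | 17 | 14 | 3% | 1% |
| 1 | 23-24 | 16 | 11% | 2% |
| 2 | 34 | 18-19 | 40% | 5% |

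(A dash means not tabulated.) With every outcome known at once, the mean treated would be 8-9. The Section 7.4.1 trigger is met at a mean of about 8, 13 and 24 treated at 0.5, 1 and 2 per week.

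**Sensitivity.** The share crossing only after all 40 are treated, as written, at 0.5/1/2 per week:
- 1/4/11% if onset is twice as fast.
- 3/9/21% with an assumed 8-week pause after participant 20.

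A separate run used other onset shapes, a true rate of 50% and looks from the third participant. Mean treated, as written against weighted:
- 35-day window: 9.4 against 8.6 at 1 per month; 19.8 against 11.7 at 8 per month.
- 12-week window: 10.8 against 8.9; 31.1 against 13.9.
- 100-day window: 12.1 against 9.3; 36.5 against 18.2.

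Direction and dependence on accrual hold throughout. Only the size changes.

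**The case against.** The strongest reply is that the table does not decide alone. It is advisory, and the plan already allows other posteriors to be calculated. The study is open label. Section 5.1.6 has SMT signal detection at least monthly and investigator calls at least monthly in expansion. Section 5.1.2 has weekly visits for the first 8 weeks, Section 7.2 alternates assignment between open doses in Parts 2A and 2B, and Section 10.3.8 allows enrolment to pause. Reviewers can see who was dosed last week. All of this stands, and it limits the consequence. None of it says how pending participants are to be counted, and the one sentence that addresses evaluability counts them in full.

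Second, the Section 7.4.1 trigger is met before the weighted rule at 0.5 and 1 per week, and later only at about 2 per week. That also stands. The trigger is discretionary, however. It uses the same treated denominator, and it can fire on very few participants: one event in two is already above 33%.

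Third, a true 45% is a tail case. Part 2 doses must have been tolerable in Part 1 and not exceed the MTD. The overdose control in Section 10.1.1 caps the posterior probability of a DLT rate of 33% or more at 35%. This is accepted.

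A reader might go further and infer that safety oversight in Part 2 fails, or that the SMT cannot act in time. The documents do not support that, because oversight rests on more than this calculation.

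**Conclusion.** The point holds in a limited form. As written, the rule gives too low a posterior while follow-up is pending, and the enrolment-halt boundary is crossed late. The direction needs no assumption. The size rests on assumed accrual, a borrowed onset distribution and a high true rate. At a true 45% it is about one participant at 0.25 per week, about three at 0.5, seven to eight at 1, and roughly fifteen at 2.

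It would be wrong to read this as an error in the 16/40 boundary. That figure reproduces and is correct once all 40 have been followed; the problem is confined to looks made before then. Severity is minor to moderate: a worthwhile improvement to a safety signal.

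**What to change.** In Section 10.3.8.1, leave the prior, 33%, 0.80, Table 10.3.8.1-1, the non-binding status and the Section 7.4.1 trigger unchanged, and add:

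1. A sponsor-defined observation window for Part 2, used for this calculation only and supported by the Part 1 onset data.
2. At each review, a second posterior for the SMT, Beta(0.5+n, 0.5+sum of weights). Each toxicity counts as 1 at once, and each event-free participant counts as the fraction of the window completed, up to 1. Calculate it directly, because fractional weights do not fit the table's integer rows.
3. A stated minimum number treated before it applies (10 was used above). A weighted posterior above 0.80 is then an additional prompt for the same temporary, non-binding halt and SMT review. Because the table still runs from participant 1, no halt comes later than now.
4. Operating characteristics under the sponsor's expected accrual and a range of onset windows, at true rates including 20%, 33% and 45%.

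Do not count toxicities at once while withholding non-events until a window closes. With a 5-week window, that rule halts 33/39/52% of the time at a true 20% (0.5/1/2 per week).

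The drafting cost is a few sentences and one table. The statistical cost is more temporary halts, again at 0.5/1/2 per week:
- True 20%: about 15/15/18% against 10/5/2% as written. The same boundary with complete follow-up gives 28-29%. A minimum of 6 instead of 10 gives 20/21/24%.
- True 33%: about 54/52/55% against 43/27/10%.

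The window matters. Twelve-week weights when onset ends by week 6 overcorrect, with halts of 20/28/40% at a true 20%, against 17/16/16% with a matching window. Six-week weights when onset runs to week 12 lose part of the gain: 2/5/18% then cross only after all 40 are treated at a true 45%, against 1/2/5%.

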**Table 10.3.8.1-1: Monitoring Boundaries for Treatment-related Toxicities Meeting DLT Criteria in Part 2**

Number of Evaluable Participants: Treated Part 2 Participants (Cumulative)	Critical Region: At or Above Number of Part 2 Participants Who Experience Treatment-related Toxicities Meeting the DLT Criteria (Defined in Section 7.4.1)
1	
2	
3	
4	
5	
6	
7	
8	
9	
10	
11	
12	
13	
14	
15	
16	
17	
18	
19	
20	
21	
22	
23	
24	
25	
26	
27	
28	
29	
30	
31	
32	
33	
34	
35	
36	
37	
38	
39	
40	

**Table 10.3.8.1-1: Monitoring Boundaries for Treatment-related Toxicities Meeting DLT Criteria in Part 2**

Number of Evaluable Participants: Treated Part 2 Participants (Cumulative)	Critical Region: At or Above Number of Part 2 Participants Who Experience Treatment-related Toxicities Meeting the DLT Criteria (Defined in Section 7.4.1)

Abbreviation: DLT = dose-limiting toxicity.

These boundaries can be applied on a continuous basis and are intended to assist the clinical interpretation. Other parameters may be considered and other posterior probabilities and boundaries may be calculated. Recommendations from interim monitoring calculations are not binding, and the totality of the data will be considered for decisions by SMT.

**12 APPENDICES**

## APPENDIX 1 ABBREVIATIONS AND TRADEMARKS

Term	Definition
3L/4L	3rd/4th line
ADA	anti-drug antibody
ADME	absorption, distribution, metabolism, and excretion
AE	adverse event
AI_AUC	AUC Accumulation Index; ratio of AUC(TAU) at steady state to AUC(TAU) after the first dose
AI_Cmax	Cmax Accumulation Index; ratio of Cmax at steady state to Cmax after the first dose
ALK	anaplastic lymphoma kinase
ALP	alkaline phosphatase
ALT	alanine aminotransferase
AR	additional research
ART	antiretroviral therapy
AST	aspartate aminotransferase
AT	aminotransaminase
AUC	area under the concentration-time curve
AUC(INF)	area under the concentration-time curve from time zero extrapolated to infinite time
AUC(0-T)	area under the concentration-time curve from time zero to the time of the last quantifiable concentration
AUC(TAU)	area under the concentration-time curve in one dosing interval
BA	bioavailability
BICR	blinded independent central review
BLRM	Bayesian Logistic Regression Model
BLRMc-MTD	Bayesian Logistic Regression Model-copula recommended maximum tolerated dose
BLRM-MTD	Bayesian Logistic Regression Model-recommended maximum tolerated dose
BMS	Bristol-Myers Squibb
BOR	best overall response

Term	Definition
BUN	blood urea nitrogen
BW	body weight
C	Cycle
Cavg	average concentration
Cavgss	average steady-state concentration
CBC	complete blood count
CD	cluster of differentiation
CFR	Code of Federal Regulations
CHMP	Committee for Medicinal Products for Human Use
CI	confidence interval
CL	clearance
CLT	total body clearance
Cmax	maximum observed concentration
Cmin	minimum observed concentration
CNS	central nervous system
CONSORT	Consolidated Standards of Reporting Trials
COVID-19	coronavirus disease 2019
CR	complete response
CRC	colorectal cancer
CrCl	creatinine clearance
CRF	case report form
CT	computed tomography
CTAg	Clinical Trial Agreement
Ctau	concentration in a dosing interval (eg, concentration at 24 hours, concentration at 12 hours, etc.)
CTCAE	Common Terminology Criteria for Adverse Events
CTLA-4	cytotoxic T-lymphocyte-associated protein 4
Ctrough	trough-observed plasma concentration
D	Day

Term	Definition
DILI	drug-induced liver injury
DLT	dose-limiting toxicity
DMC	Data Monitoring Committee
dMMR	mismatch repair deficient
DNA	deoxyribonucleic acid
DOR	duration of response
DRESS	drug reaction with eosinophilia and systemic symptoms
EC50	half-maximal effective concentration
ECG	electrocardiogram
ECOG	Eastern Cooperative Oncology Group
eCRF	electronic case report form
EDC	electronic data capture
eg	exempli gratia (for example)
eGFR	estimated glomerular filtration rate
EGFR	epidermal growth factor receptor
ELISA	enzyme-linked immunosorbent assay
EOI	end of infusion
EOT	end of treatment
EQ-5D-VAS	EQ-5D Visual Analog Scale
EQ-5D-3L	3-Level EQ-5D
EQ-5D-5L	5-Level EQ-5D
ER	exposure-response
EU	European Union
EWOC	escalation with overdose control
FACIT GP5	Functional Assessment of Chronic Illness Therapy, General Physical item
Fc $\gamma$ R	Fc gamma receptor
FDA	Food and Drug Administration
FIH	first in human

Term	Definition
FSH	follicle stimulating hormone
GBS	Guillain-Barre Syndrome
GCP	Good Clinical Practice
GI	gastrointestinal
GLP	good laboratory practice
GMR	geometric mean ratio
h	hour
HBsAg	hepatitis B surface antigen
HBV	hepatitis B virus
HCC	hepatocellular carcinoma
hCG	human chorionic gonadotrophin
HCV	hepatitis C virus
HER2	human epidermal growth factor receptor 2
HFSR	hand-foot skin reaction
HIV	human immunodeficiency virus
HNSTD	highest non-severely toxic dose
HPV	human papilloma virus
HR	hazard ratio
HRQoL	health-related quality of life
IB	Investigator Brochure
ICF	informed consent form
ICH	International Conference on Harmonisation
ie	id est (that is)
IEC	Independent Ethics Committee
IFN	interferon
Ig	immunoglobulin
IgG	immunoglobulin G
IL	interleukin
imAE	immune-mediated adverse event

Term	Definition
IMP	investigational medicinal product
INR	international normalized ratio
I-O	immuno-oncology
IP	investigational product
IPRES	Innate PD-1 RESistance
IQR	interquartile range
irAE	immune-related adverse event
IRB	Institutional Review Board
iRECIST	modified Response Evaluation Criteria in Solid Tumors in cancer immunotherapy trials
IRT	Interactive Response Technology
IU	International Unit
IUS	intrauterine hormone-releasing system
IV	intravenous
kg	kilogram
KLH	keyhole limpet hemocyanin
KRAS	Kirsten rat sarcoma virus
L	liter
LAM	lactation amenorrhea method
LDH	lactate dehydrogenase
mAb	monoclonal antibody
mCRC	metastatic colorectal cancer
MedDRA	Medical Dictionary for Regulatory Activities
mg	milligram
MG	Myasthenia Gravis
min	minute
mL	milliliter

Term	Definition
MMR	measles, mumps, rubella
MRI	magnetic resonance imaging
MSI-H	microsatellite instability high
MSS	microsatellite stable
MTD	maximum tolerated dose
μg	microgram
N	number of participants or observations
NCI	National Cancer Institute
NF	non-fucosylated
ng	nanogram
NSCLC	non-small cell lung cancer
NSCLC-SAQ	Non-small Cell Lung Cancer Symptom Assessment Questionnaire
ORR	objective response rate
OS	overall survival
OSR	overall survival rate
PBMC	peripheral blood mononuclear cell
PBS	phosphate buffered saline
PCR	polymerase chain reaction
PD	progressive disease
PD-1	programmed cell death 1
p-DILI	potential drug-induced liver injury
PD-L1	programmed death ligand 1
PD-L2	programmed death ligand 2
PE	physical examination
PET	positron emission tomography

Term	Definition
PFS	progression-free survival
PFSR	progression-free survival rate
PI	prediction interval
PID	participant identification number
PK	pharmacokinetics
pMMR	proficient mismatch repair
PPK	population pharmacokinetics
PR	partial response
PRO	patient-reported outcome
Q2W	every 2 weeks
Q3W	every 3 weeks
Q6W	every 6 weeks
Q12W	every 12 weeks
QTc	QT interval corrected
QTcF	QT interval corrected for heart rate using Fridericia's formula
RCC	renal cell carcinoma
RECIST	Response Evaluation Criteria in Solid Tumors
REMS	Risk Evaluation and Mitigation Strategy
RNA	ribonucleic acid
RP2D	recommended Phase 2 dose
RT-PCR	reverse transcription polymerase chain reaction
SAE	serious adverse event
SARS-CoV-2	severe acute respiratory syndrome coronavirus 2
SCCHN	squamous cell carcinoma of the head and neck

Term	Definition
SD	stable disease
SJS	Stevens-Johnson syndrome
SmPC	summary of product characteristics
SMT	Safety Management Team
SNP	single nucleotide polymorphism
SUSAR	suspected, unexpected serious adverse reaction
T.bili	total bilirubin
TEN	toxic epidermal necrolysis
T-HALF	half-life
Tmax	time of maximum observed concentration
TNBC	triple-negative breast cancer
TNF- $\alpha$	tumor necrosis factor alpha
TRAE	treatment-related adverse event
Treg	T-regulatory cell
TSH	thyroid stimulating hormone
TTR	time to response
ULN	upper limit of normal
US	United States
USPI	United States Prescribing Information
V ss	apparent volume of distribution at steady state
V z	volume of distribution of terminal phase (if IV and if multi-exponential decline)
WBC	white blood cell
WOCBP	women of childbearing potential
WWPS	Worldwide Patient Safety

